 - AST, ALT, or bilirubin abnormalities that meet DLT criteria ([Section 3.1.6](#)) (In most cases of AST or ALT elevation meeting DLT criteria study drugs will be permanently discontinued. If the investigator determines a possible favorable benefit/risk ratio that warrants continuation of study drugs, a discussion between the investigator and the BMS Medical Monitor/designee must occur).
 - Elevated troponin that meets DLT criteria ([Section 3.1.6](#)).

- Grade 3 drug-related endocrinopathies adequately controlled with only physiologic hormone replacement do not require discontinuation.
- Any event that leads to dosing delays lasting > 6 weeks from the previous dose **requires discontinuation** with the following **exceptions**:
 - Dosing delays to allow for prolonged steroid tapers to manage drug-related AEs are allowed. Prior to re-initiating treatment in a subject with a dosing interruption lasting > 6 weeks after the previous dose the BMS Medical Monitor must be consulted. Tumor assessments should continue as per protocol even if dosing is delayed. Periodic study visits to assess safety and laboratory studies should also continue every 6 weeks or more frequently if clinically indicated during such dosing delays.
 - Dosing delays lasting > 6 weeks from the previous dose that occur for non-drug-related reasons may be allowed if approved by the BMS Medical Monitor. Prior to re-initiating treatment in a subject with a dosing delay lasting > 6 weeks from the previous dose, the BMS Medical Monitor must be consulted. Tumor assessments should continue as per protocol even if dosing is delayed and subjects must otherwise meet the criteria for continued treatment at the time re-initiation of study therapy is considered. Periodic study visits to assess safety and laboratory studies should also continue every 6 weeks or more frequently if clinically indicated during such dosing delays.
- Any adverse event, laboratory abnormality, or intercurrent illness which, in the judgment of the Investigator, presents a substantial clinical risk to the subject with continued relatlimab or nivolumab dosing.
- PD (see also [Section 4.3.4](#) for details regarding continuing treatment beyond initial assessment of PD).
- Clinical deterioration as assessed by the Investigator.
- Completion of the maximum number of twelve 8-week cycles.

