5.5.1 Pharmacokinetics - Collection and Processing

Pharmacokinetic blood samples will be drawn from study subjects receiving relatlimab as monotherapy or in combination with nivolumab at the time points indicated in Table 5.5.1-1 and Table 5.5.1-2. All time points are relative to the start of study drug administration. All samples collected pre-dose should be taken within 30 minutes before the start of dose administration. End-of-infusion samples should be taken just prior to the end of infusion (preferably within 2 minutes) from the contralateral arm (ie, the arm not used for the infusion). On-treatment samples are intended to be drawn relative to actual dosing days. If a dose occurs on a different day within the cycle due to minor schedule adjustments or dose delays, PK samples should be adjusted accordingly. Further details of sample collection, processing, and shipment will be provided in the Laboratory Procedures Manual.

Table 5.5.1-1: PK and ADA Sampling Schedule for Relatlimab and Nivolumab in all Subjects in Part A, B, C and ██████ Subjects in Part D and for Cohorts with Re-Challenge

Study Day of Sample Collection (1 Cycle = 56 Days [8 Weeks])	Event	Time (Relative to Start of Infusion) Hour: Min	Relatlimab PK Sample (All Subjects)	Relatlimab ADA Sample (All Subjects)	Nivolumab PK Sample (Part C & D Only)	Nivolumab ADA Sample (Part C & D Only)
Cycle 1						
1	predose ^a	00:00	X	X	X	X
1	EOI ^b	01:00	X		X	
1		04:00	X			
2		24:00	X			
3-5		48:00 - 96:00 ^c	X			
7-9		144:00 - 192:00 ^c	X			
15	predose ^a	00:00	X	X	X	X
29	predose ^a	00:00	X	X	X	X
43	predose ^a	00:00	X		X	
Cycle 2						
1	predose ^a	00:00	X	X	X	X
1	EOI ^b	01:00	X		X	
15	predose ^a	00:00	X		X	
29	predose ^a	00:00	X		X	
Cycle 3						
1	predose ^a	00:00	X	X	X	X
1	EOI ^b	01:00	X		X	

Table 5.5.1-1: PK and ADA Sampling Schedule for Relatlimab and Nivolumab in all Subjects in Part A, B, C and ██████ Subjects in Part D and for Cohorts with Re-Challenge

Study Day of Sample Collection (1 Cycle = 56 Days [8 Weeks])	Event	Time (Relative to Start of Infusion) Hour: Min	Relatlimab PK Sample (All Subjects)	Relatlimab ADA Sample (All Subjects)	Nivolumab PK Sample (Part C & D Only)	Nivolumab ADA Sample (Part C & D Only)
1		04:00	X			
2		24:00	X			
3-5		48:00 - 96:00 ^b	X			
7-9		144:00 - 192:00 ^b	X			
15	predose ^a	00:00	X		X	
Subsequent Odd # Treatment Cycles						
1	predose ^a	00:00	X	X	X	X
Follow-up Period						
FU2 ^d	FU2		X	X	X	X
FU3 ^d	FU3		X	X	X	X

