^a Predose: All predose samples for relatlimab and nivolumab should be collected within 30 minutes prior to the start of nivolumab infusion.

^b EOI: End of Infusion. For subjects receiving relatlimab in combination with nivolumab, EOI samples for both relatlimab and nivolumab should be collected after the end of relatlimab infusion (preferably within 2 minutes prior to the end of infusion). If the end of infusion is delayed to beyond the nominal infusion duration, the collection of this sample should also be delayed accordingly. EOI samples may not be collected from the same IV access as drug was administered; refer to the Laboratory Procedures Manual for additional restrictions.

^c A single PK sample is to be drawn during this time range.

^d FU2 and FU3 corresponds to 60 and 135 day follow up visit, respectively.

Table 5.5.1-2: PK and ADA Sampling Schedule for Relatlimab and Nivolumab for Dose Expansion Part D after [REDACTED] Subjects

Study Day of Sample Collection (1 Cycle = 56 Days [8 Weeks])	Event	Time (Relative to Start of Infusion) Hour: Min	Relatlimab PK Sample (All Subjects)	Relatlimab ADA Sample (All Subjects)	Nivolumab PK Sample (Part C & D Only)	Nivolumab ADA Sample (Part C & D Only)
Cycle 1						
1	predose ^a	00:00	X	X	X	X
1	EOI ^b	01:00	X		X	
15	predose ^a	00:00	X	X	X	X
29	predose ^a	00:00	X	X	X	X
43	predose ^a	00:00	X		X	
Cycle 2						
1	predose ^a	00:00	X	X	X	X
1	EOI ^b	01:00	X		X	
15	predose ^a	00:00	X		X	
Cycle 3						
1	predose ^a	00:00	X	X	X	X
1	EOI ^b	01:00	X		X	
15	predose ^a	00:00	X		X	
Subsequent Odd # Treatment Cycles						
1	predose ^a	00:00	X	X	X	X
Follow-up Period						
FU2 ^c	FU2		X	X	X	X
FU3 ^c	FU3		X	X	X	X

^a Predose: For subjects receiving relatlimab in combination with nivolumab, all predose samples for relatlimab and nivolumab should be collected within 30 minutes prior to the start of nivolumab infusion.

^b EOI: End of Infusion. For subjects receiving relatlimab in combination with nivolumab, EOI samples for both relatlimab and nivolumab should be collected after the end of relatlimab infusion (preferably within 2 minutes prior to the end of infusion). If the end of infusion is delayed to beyond the nominal infusion duration, the collection of this sample should also be delayed accordingly. EOI samples may not be collected from the same IV access as drug was administered; refer to the Laboratory Procedures Manual for additional restrictions.

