8.2 Populations for Analyses

- **All Enrolled Subjects:** All subjects who signed an informed consent form and were registered into the IVRS.
- **All Treated Subjects:** All subjects who received at least one dose of study medication. This is the primary population for safety and efficacy analyses.
- **Response-Evaluable Subjects:** All treated subjects with measurable disease at baseline and one of the following: 1) at least one post-baseline tumor assessment, 2) clinical progression, or 3) death (if death occurred within 135 days after last relatlimab dose).
- **Pharmacokinetic Subjects:** All subjects who received at least one dose of relatlimab or nivolumab and have evaluable plasma/serum concentration data.
- **Immunogenicity Subjects:** All treated subjects with relatlimab or nivolumab who have baseline and at least one post baseline immunogenicity assessment.
- **Biomarker Subjects:** All treated subjects with available biomarker data.

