8.3.2.2 Immunogenicity

Incidence of ADA to either relatlimab or nivolumab will be assessed during treatment and for up to 135 days after their last treatment in post-treatment follow-up. Baseline ADA positive subject is defined as a subject with positive seroconversion detected in the last sample before initiation of treatment. ADA-positive subject is a subject with at least one ADA-positive sample relative to baseline after initiation of the treatment.

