8.4.7 Other Analyses

8.4.7.1 Immunogenicity Analyses

A listing will be provided for all available immunogenicity data. The number and percent of subjects who meet specified endpoint definitions in the statistical analysis plan (SAP) will be summarized for each drug. To examine the potential relationship between immunogenicity and safety, a table summarizing the frequency and type of AEs of special interest may be explored by immunogenicity status. In addition, potential relationships between immunogenicity and efficacy, pharmacodynamic markers, and/or PK may also be explored.

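### If AEs or efficacy are compared by ever-positive ADA status, treatment length alone can create or hide an association

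*Combined protocol and SAP*

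**What the plan says.** Section 8.3.2.2 defines status over the whole of follow-up: "ADA-positive subject is a subject with at least one ADA-positive sample relative to baseline after initiation of the treatment". Incidence "will be assessed during treatment and for up to 135 days after their last treatment in post-treatment follow-up". The immunogenicity population in section 8.2 is "All treated subjects with relatlimab or nivolumab who have baseline and at least one post baseline immunogenicity assessment", with no minimum exposure.

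Tables 5.5.1-1 and 5.5.1-2 (section 5.5.1) give the same ADA schedule. After the baseline sample, ADA is drawn on Days 15 and 29 of Cycle 1, on Day 1 of Cycles 2 and 3, on Day 1 of the "Subsequent Odd # Treatment Cycles", and at two follow-up visits: "FU2 and FU3 corresponds to 60 and 135 day follow up visit, respectively". Section 4.3.5 ends treatment at "Completion of the maximum number of twelve 8-week cycles". Section 8.3.1 gives AEs the same window, treatment plus up to 135 days.

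Section 8.4.7.1 then says that "a table summarizing the frequency and type of AEs of special interest may be explored by immunogenicity status" and that "potential relationships between immunogenicity and efficacy, pharmacodynamic markers, and/or PK may also be explored". It states no landmark, time-dependent status or exposure adjustment. It refers to ADA endpoint definitions in a statistical analysis plan, but the document supplied contains no separate plan text.

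**The concern.** ADA status under this rule is not a baseline characteristic. It is settled by follow-up whose length depends on outcome. Progression normally ends treatment (sections 3.1 and 3.5; section 4.3.4 allows exceptions), so responders tend to be dosed, sampled and observed for AEs longer. Section 6.2.1 also stops non-serious AE collection at new anti-neoplastic therapy, which can shorten the window further for early progressors. This is immortal-time bias together with unequal exposure.

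The error can run either way. ADA may look harmful because longer-treated subjects accumulate AEs. A true loss of efficacy from ADA may be hidden because subjects must stay on treatment to be sampled often. Section 8.4.7.1 is the only place where the protocol plans to relate ADA to safety or efficacy.

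**Working it through.** The plan states no figure for this analysis, so there is none to reproduce.

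**1. Schedule, from the documents.** Inputs: the ADA time points above; four doses per 8-week cycle (section 3.1), given every two weeks; 135 days of follow-up. With c completed cycles the last dose falls (c − 1) × 56 + 42 days after the first, so the AE window is (c − 1) × 56 + 42 + 135 days.

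| Cycles completed | Post-baseline ADA samples | AE window (days) |
|---|---|---|
| 1 | 4 (D15, D29, FU2, FU3) | 177 |
| 2 | 5 | 233 |
| 3 | 6 | 289 |
| 6 | 7 | 457 |
| 12 | 10 | 793 |

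From 1 to 12 cycles that is 10/4 = 2.5 times the samples and 793/177 = 4.5 times the AE window.

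**2. Null ORR, simple model.** Assumptions, not in the documents: 40% responders, treated 5–12 cycles (uniform); non-responders treated 1–3 cycles (uniform); conversion independent of response.

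(a) Conversion probability h per 8 weeks, continuing through follow-up: P(positive | c) = 1 − (1 − h)^(c + 135/56). At h = 0.05 this averages 0.4246 in responders and 0.2018 in non-responders.
- ORR, ADA-positive: 0.4 × 0.4246 / (0.4 × 0.4246 + 0.6 × 0.2018) = 58.4%.
- ORR, ADA-negative: 0.4 × 0.5754 / (0.4 × 0.5754 + 0.6 × 0.7982) = 32.5%.
- At h = 0.02: 60.7% versus 36.9%.

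(b) Probability h per scheduled sample, counts as in step 1: 51.0% versus 35.8% at h = 0.05; 52.3% versus 38.3% at h = 0.02.

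**3. Null simulation with overlapping durations.** Assumptions: 40% responders; median treatment 48 weeks in responders and 12 weeks in non-responders, capped at 12 cycles; AE rate 0.5 per person-year; full follow-up; status by the protocol's rule and schedule. AE hazard and response are independent of ADA.

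| Seroconversion pattern | ORR, ADA+ / ADA− | AE risk ratio |
|---|---|---|
| Constant, 0.15–0.5 per year | 52–55% / 33–38% | 1.30–1.36 |
| Transient, 4% per sample | 49% / 38% | 1.20 |
| First 4 weeks only, 20% of subjects | 40% / 40% | 1.00 |

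Under constant conversion the median last dose is at week 34–40 in ADA-positive and week 14–16 in ADA-negative subjects. If half of AEs end treatment, the AE ratio falls to 1.16–1.18. If all do, it is about 1.02, but ORR still differs (50–52% versus 36–39%). Over AE rates of 0.3–2.0 per year with no AE-triggered stopping, the ratio is 1.12–1.41.

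**4. The alternatives on null data.** Events per person-time before and after the first positive sample give an AE rate ratio of 1.00–1.01. A week-16 landmark (Cycle 3 Day 1) gives an AE risk ratio of 0.99–1.01. A Cycle 2 Day 1 landmark removes the ORR gap. Under the step 3 durations, ORR among subjects still on treatment is 48% in both groups. Under those of step 2, two-thirds of non-responders remain, so it is 0.4 / (0.4 + 0.6 × 2/3) = 50% in both.

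**The case against.** **The analyses are optional and descriptive.** Both are only possibilities in section 8.4.7.1, and section 1.2 says no hypotheses are formally evaluated. The secondary objective (section 1.3.2) is to characterise relatlimab immunogenicity. The incidence summary meets it and is not touched by this bias. Section 1.4.1.4 describes relatlimab monotherapy immunogenicity as low, so the ADA-positive group may be too small to interpret. All of this stands and limits the weight of the point. It does not make a table safe to read if it is produced.

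**A statistical analysis plan may already deal with it.** Section 8.4.7.1 defers ADA endpoint definitions to one. That cannot be excluded; the point concerns the protocol text supplied.

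**Stronger readings.** A reader might infer that the comparison is bound to show a false association. The documents do not support this: they give no seroconversion timing, and early conversion produces no bias. A reader might also infer that ADA-positive means long-treated and ADA-negative short-treated. FU2 and FU3 are scheduled whatever the treatment duration, so the groups overlap and differ only on average. A model with conversion only during treatment cycles gives a larger gap, 71% versus 32% at 5% per cycle under the step 2 durations. It leaves out the two follow-up samples that every subject is due.

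**Conclusion.** The point holds as a conditional one. If AEs of special interest or efficacy are compared by ever-positive ADA status, as section 8.4.7.1 permits, the result can reflect time on treatment and not ADA, in either direction.

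With 40% responders and conversion continuing over time, null ORR is roughly 50–60% in ADA-positive and 33–38% in ADA-negative subjects. The AE risk ratio is about 1.3 when AEs do not stop treatment and close to 1 when they all do. If seroconversion is confined to the first weeks there is no gap. These sizes rest on assumed response rates, durations, AE rates and conversion patterns, because the trial's own are redacted or absent. Only the sample counts and window lengths come from the documents.

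**What to change.** In section 8.4.7.1, state that any comparison of AEs or efficacy by ADA status will treat ADA as time-dependent: AEs per person-time before and after the first positive sample, and a time-dependent covariate for PFS and DOR. Add a landmark table as a supporting analysis, for example at Cycle 2 Day 1 or Cycle 3 Day 1, in subjects still on study and counting later events only. Keep ever-positive status for ADA incidence alone.

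The samples needed are in both sampling tables, so the cost is wording and slightly more analysis work. The landmark table counts late converters as negative and omits AEs, responses and progressions before the landmark. That is why time-dependent status should be the main analysis.

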8.5 Interim Analyses

Data emerging from this open-label exploratory study may be needed for safety monitoring, and to make timely decisions about adjustments to study procedures, including potential early termination of the study. Analyses will only consist of listings, summaries, and graphs of the available data. No formal inferences requiring any adjustment to statistical significance level will be performed.

9 STUDY MANAGEMENT

9.1 Compliance

9.1.1 *Compliance with the Protocol and Protocol Revisions*

The study shall be conducted as described in this approved protocol. All revisions to the protocol must be discussed with, and be prepared by, BMS. The investigator should not implement any deviation or change to the protocol without prior review and documented approval/favorable opinion from the IRB/IEC of an amendment, except where necessary to eliminate an immediate hazard(s) to study subjects.

If a deviation or change to a protocol is implemented to eliminate an immediate hazard(s) prior to obtaining IRB/IEC approval/favorable opinion, as soon as possible the deviation or change will be submitted to:

- IRB/IEC for review and approval/favorable opinion
- BMS
- Regulatory Authority(ies), if required by local regulations

Documentation of approval signed by the chairperson or designee of the IRB(s)/IEC(s) must be sent to BMS.

If an amendment substantially alters the study design or increases the potential risk to the subject: (1) the consent form must be revised and submitted to the IRB(s)/IEC(s) for review and approval/favorable opinion; (2) the revised form must be used to obtain consent from subjects currently enrolled in the study if they are affected by the amendment; and (3) the new form must be used to obtain consent from new subjects prior to enrollment.

If the revision is done via an administrative letter, investigators must inform their IRB(s)/IEC(s).

9.1.2 *Monitoring*

Representatives of BMS must be allowed to visit all study site locations periodically to assess the data quality and study integrity. On site they will review study records and directly compare them with source documents, discuss the conduct of the study with the investigator, and verify that the facilities remain acceptable.

In addition, the study may be evaluated by BMS internal auditors and government inspectors who must be allowed access to CRFs, source documents, other study files, and study facilities. BMS audit reports will be kept confidential.

The investigator must notify BMS promptly of any inspections scheduled by regulatory authorities, and promptly forward copies of inspection reports to BMS.

9.1.3 *Investigational Site Training*

BMS will provide quality investigational staff training prior to study initiation. Training topics will include but are not limited to: GCP, AE reporting, study details and procedure, electronic CRFs, study documentation, informed consent, and enrollment of WOCBP.

9.2 Records

9.2.1 Records Retention

The investigator must retain all study records and source documents for the maximum period required by applicable regulations and guidelines, or institution procedures, or for the period specified by BMS, whichever is longer. The investigator must contact BMS prior to destroying any records associated with the study.

BMS will notify the investigator when the study records are no longer needed.

If the investigator withdraws from the study (eg, relocation, retirement), the records shall be transferred to a mutually agreed upon designee (eg, another investigator, IRB). Notice of such transfer will be given in writing to BMS.

9.2.2 Study Drug Records

It is the responsibility of the investigator to ensure that a current disposition record of investigational product (those supplied by BMS) is maintained at each study site where study drug is inventoried and dispensed. Records or logs must comply with applicable regulations and guidelines and should include:

- amount received and placed in storage area
- amount currently in storage area
- label identification number or batch number
- amount dispensed to and returned by each subject, including unique subject identifiers
- amount transferred to another area/site for dispensing or storage
- non-study disposition (eg, lost, wasted)
- amount destroyed at study site, if applicable
- amount returned to BMS
- retain samples for bioavailability/bioequivalence, if applicable
- dates and initials of person responsible for Investigational Product dispensing/accountability, as per the Delegation of Authority Form.

BMS will provide forms to facilitate inventory control if the investigational site does not have an established system that meets these requirements.

9.2.3 Case Report Forms

An investigator is required to prepare and maintain adequate and accurate case histories designed to record all observations and other data pertinent to the investigation on each individual treated or entered as a control in the investigation. Data that are derived from source documents and reported on the CRF must be consistent with the source documents or the discrepancies must be explained. Additional clinical information may be collected and analyzed in an effort to enhance understanding of product safety. CRFs may be requested for AEs and/or laboratory abnormalities that are reported or identified during the course of the study.

For sites using the BMS electronic data capture tool, electronic CRFs will be prepared for all data collection fields except for fields specific to SAEs and pregnancy, which will be reported on the paper or electronic SAE form and Pregnancy Surveillance form, respectively. Spaces may be left blank only in those circumstances permitted by study-specific CRF completion guidelines provided by BMS.

The confidentiality of records that could identify subjects must be protected, respecting the privacy and confidentiality rules in accordance with the applicable regulatory requirement(s).

The investigator will maintain a signature sheet to document signatures and initials of all persons authorized to make entries and/or corrections on CRFs.

The completed CRF, including any paper or electronic SAE/pregnancy CRFs, must be promptly reviewed, signed, and dated by the investigator or qualified physician who is a subinvestigator and who is delegated this task on the Delegation of Authority Form. For electronic CRFs, review and approval/signature is completed electronically through the BMS electronic data capture tool. The investigator must retain a copy of the CRFs including records of the changes and corrections.

Each individual electronically signing electronic CRFs must meet BMS training requirements and must only access the BMS electronic data capture tool using the unique user account provided by BMS. User accounts are not to be shared or reassigned to other individuals.

